Program Director/Principal Investigator (Last, First, Middle): **[name]**

Evaluation of a nonopioid recovery pathway after percutaneous nephrolithotomy

NCT04597619

[name]

Document last updated: 09/07/2022

Background:

Urologic surgery has played a role in the perpetuation of the opioid epidemic in the United States with the continued use of opioid medications despite evidence showing the efficacy of nonopioid protocols.^{1,2} The use of opioid medications in the postoperative setting has been shown to be an important factor for chronic use, and often, outpatient surgery may be a patient's initial exposure.³ Urologic surgery is not immune from this as recent studies have demonstrated that nearly one-in-16 opioid-naive patients develop new persistent opioid use after ureteroscopy for nephrolithiasis.⁴ In addition, patients with kidney stones may have a higher risk for long-term opioid use than non-stone formers.^{5,6} Recent studies have emphasized the efficacy of nonopioid protocols for outpatient urologic procedures.⁷ Our own preliminary data has demonstrated that the vast majority of patients can be discharged without any opioid prescriptions after outpatient ureteroscopy with no impact on outpatient healthcare resources.⁸

What is not known, however, is whether other minimally invasive urologic procedures which historically have used opioids for postoperative pain control are also amenable to nonopioid care pathways. Percutaneous nephrolithotomy (PCNL) is a minimally invasive procedure performed by urologists for larger stone burden in the kidney. It typically is followed by an overnight stay in the hospital for observation. **Our hypothesis is that a novel nonopioid pathway after PCNL is both feasible and safe and will reduce postoperative prescriptions for opioids without impacting clinical outcomes, patient satisfaction or outpatient resources.**

Evaluation of a nonopioid recovery pathway after percutaneous nephrolithotomy has three specific aims:

Demonstrate feasibility and acceptability of the novel nonopioid protocol and describe the barriers to enrollment and reasons for drop out.

Measures: The feasibility of the protocol will be measured by dropout of enrolled patients and the acceptability of protocol will be measured by number of enrolled patients / patients approached and patient satisfaction via standardized validated questionnaire (Ureteral Stent Symptom Questionnaire).

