Patients referred to The Miriam Hospital Kidney Stone Center / Brown Urology for complex kidney stone disease and scheduled for percutaneous nephrolithotomy (PCNL) during the active study enrollment period who meet inclusion criteria will be offered participation in the study. Our center performs approximately 75 PCNLs yearly and we anticipate enrolling 25 patients, which will be adequate to demonstrate the safety and feasibility of the protocol (see Statistical Design and Power).

Urology housestaff and an attending urologist are on call 24 hours a day. Patients will be encouraged to reach out via telephone for questions concerning the study or continued participation. At the postoperative follow up visit (scheduled for 7-10 days after surgery), the research assistant will administer the Ureteral Stent Symptom Score (USSQ), a validated questionnaire regarding postoperative pain control. This will also function to establish continued participation in the study. Patients will complete their participation in the study 30 days after surgery.

Study Timeline:

Two months after notice of award, eligible patients scheduled for percutaneous nephrolithotomy (PCNL) will be offered participation in the study. The study will accrue patients through for one year or until the enrollment goal (25 patients) has been met. Statistical analysis will be performed following accrual and initial findings will

be summarized and reported per protocol to COBRE Opioids and Overdose as well as ClinicalTrials.gov approximately 24 months after notice of award.

Protocol:

Informed consent will be obtained at the time of consent for surgery in the outpatient urologic clinic setting. Either the principal investigator or the trained research assistant (TBA) will conduct the consenting process. Consent will be in written form. A description of the study will be described by the physician or research assistant and will be provided in written form. Patients deemed able to consent for the surgery will have capacity to consent to participation in the study. Patients not able to consent to surgery will not be eligible for the study. The consent process will inform a volunteer about the study, indicate the participation is voluntary and he/she has the right to stop at any time. Risks will be enumerated in the informed consent form and described verbally during the consent process.

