- Feasibility of the protocol (number of enrolled patients / patients approached),
- Adherence to and acceptability of the protocol (dropout of enrolled patients and patient satisfaction)

- Adverse events (AEs) while inpatient and following discharge
- Discharge following PCNL without prescription for opioid medications

Secondary study outcomes:

- Postoperative inpatient opioid utilization (morphine mEq / kg / day)
- Opioid prescriptions written at time of discharge (morphine mEq / kg / day)
- Ureteral Stent Symptom Questionnaire (USSQ)¹⁴ scores at postoperative visit
- Non-opioid medications given for pain
- Length of stay (hours)
- Calls to clinic for pain / discomfort within 30 days
- Requests for refills or opioid prescriptions within 30 days
- Presentations to ED for pain within 30 days

Data Analysis:

The protocol will be assessed for feasibility of implementation and safety through analysis of acceptability (number of enrolled patients / patients approached), Adherence to and acceptability of the protocol (dropout of enrolled patients and patient satisfaction via a validated questionnaire (USSQ) and adverse events (AEs) while inpatient and following discharge. Statistical analysis of the pre- and post- intervention groups will be performed to assess for significant overall reduction in opioid prescriptions. Analysis of the patient characteristics and primary / secondary outcomes of the patients will be used to assess potential reasons for opioid necessity following PCNL. A Redcap database designed with assistance from the Data and Research Methods core will be maintained in accordance with the institutional data safety plan.

Statistical Analysis Plan:

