This is a pragmatic pilot study which will prospectively compare a cohort of 15 patients undergoing PCNL prior to implementation of the novel nonopioid pathway to 15 patients undergoing the same procedure utilizing the novel nonopioid pathway. A historical cohort of patients was analyzed to determine the study population size needed to achieve our goals. Sixty-four patients underwent PCNL at The Miriam Hospital in 2018 and approximately 80% of patients were discharged home with a prescription for opioid pain medication (20% opioid-free discharge rate). Current standard of care following PCNL remains the routine prescription of opioid medications for pain control. Since PCNL is a more invasive procedure than ureteroscopy and is a non-natural orifice surgery, we expect to reduce opioid prescriptions from 80% to 50% (50% opioid-free discharge rate). To power a study with a beta of 0.8 and an alpha of 0.05 requires only a small sample size of 13 patients with this large reduction. In order to account for patient drop out and protocol non-adherence, we plan to enroll 30 patients in our pilot study.

The subject population will be adult patients referred to The Miriam Hospital Kidney Stone Center (Lifespan – Providence, RI) and Brown Urology (Brown Physicians, Inc. – Providence, RI) for complex kidney stone disease and scheduled for percutaneous nephrolithotomy (PCNL) during the active study enrollment period who meet inclusion criteria. As the prevalence of nephrolithiasis in the United States is seen more in men (1.4:1 male vs female),¹³ we anticipate our patient population to include more men than women. The risk difference between men and women, however, has been narrowing and we would expect that given our anticipated study population size of 30 patients, approximately 12-15 patients will be women. Nephrolithiasis affects all races and given the diverse population of the greater Providence, RI region, we anticipate a significant portion of our study population to be of non-white race. Every effort will be made to offer participation to eligible women and minorities.

The protocol will be assessed for feasibility of implementation and safety through analysis of acceptability (number of enrolled patients / patients approached), adherence to and acceptability of the protocol (dropout of

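### The statement that 25 patients are enough to demonstrate safety and feasibility has no support in the plan, conflicts with the planned 30, and should be restated as estimation with exact confidence intervals

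*Combined protocol and SAP*

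**What the plan says.** The Recruitment and retention plan states: "we anticipate enrolling 25 patients, which will be adequate to demonstrate the safety and feasibility of the protocol (see Statistical Design and Power". Study Timeline repeats the figure, with accrual for one year or "until the enrollment goal (25 patients) has been met". Inclusion of Women and Minorities also uses 25.

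Study Design and the Statistical Analysis Plan give a different total: "In order to account for patient drop out and protocol non-adherence, we plan to enroll 30 patients in our pilot study". They describe the comparison as one that will "prospectively compare a cohort of 15 patients undergoing PCNL prior to implementation of the novel nonopioid pathway to 15 patients" on the pathway. Their justification is about prescribing only: "we expect to reduce opioid prescriptions from 80% to 50% (50% opioid-free discharge rate", followed by "To power a study with a beta of 0.8 and an alpha of 0.05 requires only a small sample size of 13 patients".

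The primary outcomes include the ratio of enrolled to approached patients, drop-out of enrolled patients, and "Adverse events (AEs) while inpatient and following discharge". The specific aims ask only for a description of adverse events relative to standard care, and present the study as a pilot for a later randomised trial. The hypothesis in Background goes further: the pathway is feasible and safe and "will reduce postoperative prescriptions for opioids without impacting clinical outcomes, patient satisfaction or outpatient resources".

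**The concern.** The Recruitment and retention plan asserts a property of the design and refers the reader elsewhere for the evidence. The heading it cites is not in the document, and the sample-size text that does exist answers another question. Feasibility and adverse events are nonetheless primary outcomes.

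The hypothesis also contains statements of no difference (outcomes, satisfaction, outpatient resources), while the plan sets no margin and specifies no confidence intervals. If the adequacy sentence stands, a cohort with few or no events could be taken to have settled safety, and a non-significant difference between two small cohorts to have shown no impact. Either reading could then carry into the planned randomised trial.

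**Working it through.** **1. The plan's own figures.** The 25 comes with no inputs (no expected event rate, acceptable limit, feasibility criterion or interval width), so there is nothing to reproduce.

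The 13 has inputs: 80% against 50%, alpha 0.05, and the stated beta of 0.8 read as power 0.80.
- Two cohorts, two-sided, pooled variance: n per cohort = [1.960·√(2·0.65·0.35) + 0.842·√(0.8·0.2 + 0.5·0.5)]² / 0.30² = (1.322 + 0.539)² / 0.09 = 38.5, so 39. One-sided, it is 31.
- One sample against a fixed 20% opioid-free rate, one-sided: n = [(1.645·√(0.2·0.8) + 0.842·√(0.5·0.5)) / 0.30]² = (1.079 / 0.30)² = 12.9, so 13.

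The 13 thus matches a one-sample calculation, not the two-cohort design described. For the present point, what matters is that neither route involves adverse events, drop-out or enrolment, and neither leads to 25.

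**2. What the sections supply for each claimed property.**

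| Property | Primary outcome? | Expected rate, limit or threshold | Precision or power |
|---|---|---|---|
| Opioid-free discharge | Yes | 20% to 50% | n = 13 stated |
| Adverse events | Yes | None | None |
| Enrolled / approached | Yes | None; number approached not given | None |
| Drop-out of enrolled patients | Yes | None | None |

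**3. Precision for adverse events on the pathway.** The exact (Clopper-Pearson) two-sided 95% upper limit with 0 events in n is 1 − 0.025^(1/n). With 1 event it is the p that solves (1 − p)^n + n·p·(1 − p)^(n−1) = 0.025. For example, n = 15 with no events gives 1 − 0.025^(1/15) = 1 − 0.782 = 21.8%.

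| Pathway patients | Source | 0 events | 1 event |
|---|---|---|---|
| 15 | Study Design, Statistical Analysis Plan | 21.8% | 31.9% |
| 13 | 25 split evenly (assumption) | 24.7% | 36.0% |
| 12 | 25 split evenly (assumption) | 26.5% | 38.5% |
| 25 | all 25 on the pathway (assumption) | 13.7% | 20.4% |

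The Recruitment and retention plan does not say how the 25 divide between cohorts, so the last three rows are a range and not a reading of the plan. As a further guide, a true event rate of 10% would leave 15 patients event-free with probability 0.9^15 = 21%.

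**4. Feasibility has other denominators.** Drop-out is defined on enrolled patients, so on 25 or 30. With no drop-outs the upper limit would be 13.7% or 11.6%. Enrolled over approached has the number approached as its denominator; that number is not given, so no interval can be computed in advance.

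**5. Differences between cohorts.** Taking 15 per cohort and an assumed common rate p (for example, emergency visits), the approximate 95% half-width is 1.96·√(2p(1 − p)/15). This gives ±16 points at p = 5%, ±21 at 10% and ±29 at 20%. The normal approximation is rough at this size, but the order of magnitude is clear.

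**The case against.** The strongest reply is that this is a pilot whose safety aim is descriptive, so the sentence is loose wording and not a design flaw. Sample-size text does exist under Study Design and the Statistical Analysis Plan, so the reference is a wrong heading. Much of this stands. The reply still does not rescue the claim, because the text under those headings is silent on safety and feasibility and uses a different total.

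A reader might infer four stronger things, which the documents do not support:

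- **That the claim is false.** An upper limit of 22% fails only against a limit, and the plan states none. Adequacy cannot be judged either way.
- **That the design cannot exclude event rates of 20 to 30%.** An event-free cohort of 15 does exclude rates above 21.8%: at a true rate of 30% it would occur with probability 0.7^15 = 0.5%. Limits of 30% or more need at least one event at the cohort sizes of 12 to 15. If all 25 were on the pathway, no events would give 13.7%.
- **That feasibility also rests on the pathway cohort alone.** The stated denominators are patients approached and patients enrolled.
- **That the sponsor intends to report few events as safety shown, or non-significance as equivalence.** Nothing says so. The only significance assessment named is for opioid prescriptions, and the no-impact wording is a hypothesis. The point is that the plan does not rule such a reading out.

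**Conclusion.** The adequacy statement is unsupported: the cross-reference leads to no such heading, the existing calculation covers prescribing alone, and 25 conflicts with 30. It also promises more than the descriptive safety aim requires.

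If the pathway cohort is 15, as Study Design and the Statistical Analysis Plan state, an event-free result leaves true adverse-event rates up to 21.8% open, and a single event leaves rates up to 31.9% open. Under the two assumed uses of the 25, the corresponding limits are about 25 to 26% and 36 to 38% (even split), or 13.7% and 20.4% (all on the pathway). These limits are exact, two-sided and at the 95% level. They describe precision and are not evidence of failure, because no safety limit is given. The conclusion that the claim lacks a basis holds whichever cohort size is right.

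**What to change.** 1. Reconcile the 25 in Inclusion of Women and Minorities, the Recruitment and retention plan and Study Timeline with the 30 in Study Design and the Statistical Analysis Plan. State how many patients are in each cohort.
2. Point the cross-reference to a section that exists.
3. Replace the adequacy claim with a statement that the study will estimate feasibility and adverse-event rates, and give the exact upper limit for the reconciled pathway cohort (21.8% with no events if it is 15).
4. Report enrolled over approached, drop-out of enrolled patients and adverse-event proportions with exact 95% confidence intervals, each on its own denominator. Report differences between cohorts with confidence intervals.
5. State that a non-significant difference will not be taken as evidence that outcomes, satisfaction or outpatient resources are unaffected.

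The cost is wording and routine intervals, and a less favourable description of what the study can show. No extra patients are needed.

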vs female),¹³ we anticipate our patient population to include more men than women. The risk difference between men and women, however, has been narrowing and we would expect that given our anticipated study population size of 30 patients, approximately 12-15 patients will be women. Nephrolithiasis affects all races and given the diverse population of the greater Providence, RI region, we anticipate a significant portion of our study population to be of non-white race. Every effort will be made to offer participation to eligible women and minorities.

Inclusion and Exclusion Criteria:

Patients ≥ 18 years old undergoing primary percutaneous nephrolithotomy at the Miriam Hospital (Lifespan Network, Providence, RI) will be eligible for enrollment. Patients will be excluded if undergoing concurrent non-PCNL procedure, second-look PCNL (subsequent PCNL after primary PCNL), or present with Chronic Kidney Disease Stage ≥ 3 or eGFR < 50 mL/min/1.73m² at time of surgery. Patients with allergy to NSAIDs or have history of NSAID related GI bleeding or ulcers will be excluded.

Inclusion of Women and Minorities:

As the prevalence of nephrolithiasis in the United States is seen more in men (1.4:1 male vs female), we anticipate our patient population to include more men than women. The risk difference between men and women, however, have been narrowing and we would expect that given our anticipated study population size of 25 patients, approximately 10 patients will be women. Nephrolithiasis affects all races and given the diverse population of the greater Providence, RI region, we anticipate a significant portion of our study population to be of non-white race. Every effort will be made to offer participation to eligible women and minorities.

Inclusion of Children

Patients under the age of 18 will not be eligible for participation in the study. The study is aimed at understanding adult nephrolithiasis and the feasibility of nonopioid postoperative pain control after percutaneous nephrolithotomy, and nephrolithiasis of childhood is a distinct clinical entity not addressed by this study.

Vulnerable Subjects:

Special vulnerable populations, such as fetuses, neonates, pregnant women, children, prisoners, or institutionalized individuals will not be eligible for participation in the study.

Recruitment and retention plan:

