After written consent and enrollment, patients will undergo preoperative counseling regarding pain after PCNL in the preoperative holding area prior to surgery. The patient will then undergo percutaneous nephrolithotomy. No procedural changes will be made for study participants. The procedure will follow standard of care for PCNL. The nonopioid pathway will be discussed with the anesthesia team intraoperatively. Postoperatively, patients will be admitted to the post-anesthesia care unit (PACU) and standard of care adjunctive and analgesic medications will be administered. The patient will be admitted to the floor following surgery and postoperative specialized nonopioid PCNL pathway orders will be communicated to nursing staff via electronic medical record. The patient's pain will be treated with multimodal nonopioid analgesic agents such as cold packs, repositioning, ambulation, acetaminophen, tamsulosin, phenazopyridine, ketorolac, and oxybutynin on an as necessary basis (medications contraindicated due to allergy or intolerance will not be administered). Opioid medications **will not be withheld** for patients with severe (8-10 score on the numerical rating scale) pain. The patient's pain will be recorded by nursing staff every 4 hours as in standard of care. On postoperative day one (POD#1), the patient will be assessed for discharge as in standard of care. They will be asked about their perceived need for a prescription for opioids. If requested, the patient will be given a prescription for a limited quantity of opioids (five [5] tabs of 5mg oxycodone to be taken every 8hours only as necessary for severe 8-10 pain). Nursing staff will complete specialized nonopioid PCNL pathway instructions and patients will be given written instructions regarding medications and activity. Patients will be seen in 7-10 days for stent removal in the office per standard of care, and will complete the Ureteral Stent Symptom Questionnaire (USSQ), a validated quality of life survey for pain after kidney stone surgery.

Specific multimodal interventions of the pathway:

- Preoperative counseling script regarding pain after PCNL surgery
- Post-Anesthesia Care Unit (PACU) nursing instructions and standard recovery medications
- Perioperative pain protocol EMR orderset including medication instructions
- Tailored PCNL discharge instructions for patients and nursing staff
- Standardized discharge medication prescriptions

Primary study outcome:

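### Study Timeline closes accrual at 25 patients, but Study Design and the SAP plan 15 + 15 = 30, and neither reading of 25 fits that plan

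*Combined protocol and SAP*

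**What the plan says.** The document gives two enrolment totals, both in current text.

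**Thirty.** Study Design and the Statistical Analysis Plan (SAP) both say the study will "prospectively compare a cohort of 15 patients undergoing PCNL prior to implementation of the novel nonopioid pathway to 15 patients undergoing the same procedure" under the new pathway. After stating a requirement of 13 patients, both add: "In order to account for patient drop out and protocol non-adherence, we plan to enroll 30 patients in our pilot study". The population paragraph that follows in each repeats the total: "given our anticipated study population size of 30 patients, approximately 12-15 patients will be women".

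**Twenty-five.** Three places use this figure:

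- Inclusion of Women and Minorities: "given our anticipated study population size of 25 patients, approximately 10 patients will be women".
- Recruitment and retention plan: "we anticipate enrolling 25 patients, which will be adequate to demonstrate the safety and feasibility of the protocol (see Statistical Design and Power").
- Study Timeline, as the rule that ends accrual: "The study will accrue patients through for one year or until the enrollment goal (25 patients) has been met".

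The section that the Recruitment text cites as the basis for 25 is not found under that heading in the available text. The sample-size text that is present gives 13, 15 + 15 and 30, and never 25.

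**The concern.** The enrolment total is a figure the whole trial relies on, and here one of the two versions sits inside the accrual stop rule. Staff working from the Study Timeline would close enrolment at 25. An analyst working from the SAP expects 15 patients in each cohort.

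The planned analysis is a comparison of cohorts: "Statistical analysis of the pre- and post- intervention groups will be performed to assess for significant overall reduction in opioid prescriptions". Describing adverse events against standard of care is also one of the three specific aims. Because the stop is stated as a single overall count, with no rule by cohort and no stated order of filling, any shortfall could fall entirely on the pathway cohort, which is the group the pilot is meant to evaluate.

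**Working it through.** **1. The plan's own figures.** Inputs from Study Design and the SAP: opioid prescription at discharge 80% falling to 50%, alpha 0.05, power 0.80 (printed as beta), requirement 13, cohorts 15 and 15, total 30.

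- The 13 can be reproduced as a one-sample, one-sided normal-approximation test of 50% against a fixed 80%: n = [(1.645 × √(0.8 × 0.2) + 0.842 × √(0.5 × 0.5)) / 0.3]² = 12.93, rounded up to 13.
- 15 + 15 = 30. Going from 13 to 15 per cohort allows for 1 − 13/15 = 13% loss.

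So 30 follows from 13 plus a modest dropout allowance, if 13 is taken per cohort.

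**2. Can 25 be reached from the same inputs?**

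- As two groups of 13: 2 × 13 = 26, already above 25, with nothing left for dropout.
- As 13 inflated for dropout: this needs 1 − 13/25 = 48% loss, which is stated nowhere.
- As 25 evaluable out of 30 enrolled: excluded, because the Timeline and Recruitment text both use 25 as a number enrolled.

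**3. Reading A: 25 is the whole study.** The two sentences on women use the same phrase for the study size, once with 30 and once with 25. Each count of women matches its own total at the stated 1.4:1 ratio: 25/2.4 = 10.4 and 30/2.4 = 12.5. This makes A the more natural reading.

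- Shortfall: 30 − 25 = 5, and 5/30 = 16.7%.
- Most even split: 13 and 12. If the pre-implementation cohort fills first: 15 and 10.

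**4. Reading B: 25 is the pathway cohort only.** The Recruitment text ties 25 to safety and feasibility of the pathway, and the Protocol section describes only pathway care once a patient is enrolled: "After written consent and enrollment, patients will undergo preoperative counseling regarding pain after PCNL in the preoperative holding area prior to surgery".

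- Excess over the planned cohort: 25 − 15 = 10.
- Total: 25 + 15 = 40, a figure that appears nowhere in the document.

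**5. Size of the change, shown on adverse events.** If no events are seen in n pathway patients, the two-sided 95% Clopper-Pearson upper limit is 1 − 0.025^(1/n).

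| Pathway n | Where it arises | Upper limit |
|---|---|---|
| 15 | SAP | 21.8% |
| 13 | Reading A, even split | 24.7% |
| 12 | Reading A, even split | 26.5% |
| 10 | Reading A, pre-implementation cohort first | 30.8% |
| 25 | Reading B | 13.7% |

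The plan sets no precision target, so these limits show scale only.

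**6. Why power is not the argument.** For 80% against 50%, two-sided 0.05, going from 15/15 to 15/10 lowers power from 40.1% to 34.9% by normal approximation with pooled null variance, but raises it from 24.6% to 28.0% by Fisher's exact test. The plan does not name the test.

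**7. Share of yearly volume (about 75 procedures, Recruitment section).** 25/75 = 33%, 30/75 = 40%, 40/75 = 53%.

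**The case against.** The best case on the other side is that this is a small pilot and little turns on five patients. The feasibility outcomes (enrolled over approached, and dropout) can be estimated at 25 or at 30. Moving to 30 does not rescue the comparison: about 39 per group would be needed for 80% power with a two-sided two-group test. Under reading B the pathway estimates become more precise. The accrual stop is also not 25 alone. The one-year limit may bind first, so the shortfall is conditional and writing 30 does not guarantee 30. Finally, since 15 + 15 and 30 appear in both Study Design and the SAP, 25 may simply be a number that was not updated.

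Much of this stands. The statistical cost is modest, the zero-event limits rest on an assumed outcome, and the one-year limit is a real caveat. The stale-number explanation is plausible, but the document does not say so, and 25 occurs in three places. None of this tells staff when to stop enrolling. It is also fair to say that 25 is not derived in the available text, rather than that no derivation exists, because the Recruitment section points to a heading that cannot be found there.

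**Conclusion.** The contradiction holds and must be corrected. It lies in current text, one side of it is the accrual stop rule, and no reading of 25 agrees with 15 + 15 = 30.

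On the more natural whole-study reading, reaching the Timeline's goal closes accrual 5 patients (17%) before both SAP cohorts can be filled. On the pathway-only reading, the pathway cohort exceeds the SAP by 10 and the total is 40.

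The 15/10 split assumes that the pre-implementation cohort fills first, which the plan does not state. The shortfall of five assumes that the goal of 25 is reached within the year. The finding is about consistency and about who gets enrolled. It does not say that 30 would be an adequate size for the comparison.

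**What to change.** 1. The sponsor should first confirm what 25 counts: both cohorts, or pathway patients only.
2. If the SAP figure is intended, change 25 to 30 in the Recruitment and retention plan, the Study Timeline and Inclusion of Women and Minorities. In the last of these, use the existing estimate of 12 to 15 women. Write the accrual stop by cohort, 15 each.
3. If 25 is intended, restate the cohort sizes, the total and the dropout allowance in Study Design and the SAP, and say which cohorts 25 covers.
4. In either case, make the cross-reference in the Recruitment text point to a section that exists and contains the figure.

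Under step 2 the cost is wording in three places, plus up to five more patients than the current stop rule allows on reading A (40% rather than 33% of about 75 procedures a year). Eligibility and consent rates are not given, so the one-year limit may still end accrual early. Confirmation comes first because, if reading B was meant, changing to 30 would cut the pathway cohort from 25 to 15 and widen the zero-event limit from 13.7% to 21.8%.
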